5.6. SAFETY SET

The Safety Set will include all subjects who receive at least 1 dose of study treatment in Study APD334-308. For this set, subjects will be analyzed according to the treatment received, regardless of randomization. The Safety Set will be used for all safety analyses.

5.7. PHARMACOKINETIC SET

The Pharmacokinetic Set will include all subjects in the Safety Set with at least 1 quantifiable post-dose etrasimod concentration which is not impacted by protocol violations or events with potential to affect the etrasimod concentration.

6. GENERAL CONSIDERATIONS

6.1. Reference Start Date and Study Day

Study Day will be calculated from the reference start date and will be used to show start/stop day of assessments and events. Reference start date is defined as the date of first dose (Day 1 in study APD334-302) will appear in every listing where an assessment date or event date appears.

- If the date of the event is on or after the reference date, then:

$$\text{Study Day} = (\text{date of event} - \text{reference date}) + 1$$

- If the date of the event is prior to the reference date, then:

$$\text{Study Day} = (\text{date of event} - \text{reference date})$$

In the situation where the event date is partial or missing, event dates will be displayed as partial or missing, Study Day and any corresponding durations will appear missing in the listings.

6.2. Baseline

Subjects in Study APD334-308 will continue receiving the same study treatment of Study APD334-302. Unless otherwise specified, analysis baseline for efficacy and safety (for example in change from baseline analysis) is defined as the last non-missing measurement taken prior to the date of first dose in Study APD334-302 (including unscheduled assessments). If measurements include time (except for health-related quality of life [HRQoL] instruments), the date/time will be used to define Baseline. Otherwise, only dates will be compared. For HRQoL instruments, only the date will be used to derive Baseline. In the case where the last non-missing measurement and the date of first dose coincide and time is not collected, if the measurement was planned in the protocol to be done prior to the date of first dose, that measurement will be considered in defining Baseline.

6.3. Retests, Unscheduled Visits and Early Termination Data

For by-visit analyses and summaries, efficacy, safety, HRQoL, and biomarkers data (including scheduled, retests, unscheduled, and early termination) will be assigned to visits after the application of the windowing conventions described in Section 6.4. All measurements will be considered in summaries of abnormalities or worst-case values post Baseline.

Listings will include scheduled, unscheduled, retest, and early termination data.

6.4. Windowing Conventions

All scheduled study visits are defined relative to Study Day 1 in ADP334-302, the date of first dose in Study APD334-302. Scheduled visit windows are defined in Study APD334-308 Protocol Appendix 1. A windowing convention will be used to determine the analysis visit value for a given measurement and will be applicable for all by-visit summaries and analyses for efficacy and safety data. Refer to Table 2 for specific visit windows.

Table 2 *Visit Windows for Efficacy and Safety Analyses*

For all efficacy (except endoscopy/MMS/histology), efficacy-related biomarkers, safety labs and vital signs.	
Scheduled Study Visit (Protocol Scheduled Day)	Analysis Visit Window (Study Day)
Baseline in Study APD334-302	≤ 1
Week 12 (Day 85 ± 3) in Study APD334-302	72 to 99
Week 16 (Day 113 ± 7)	100 to 127
Week 20 (Day 141 ± 7)	128 to 155
Week 24 (Day 169 ± 7)	156 to 197
Week 32 (Day 225 ± 7)	198 to 253
Week 40 (Day 281 ± 7)	254 to 309

Week 48 (Day 337 ± 7)	310 to 351
Week 52 (Day 365 ± 7)	> 351
For endoscopy/MMS/histology/all composite endpoints that include an endoscopy component and/or RB/SF component, physician's global assessment, health-related quality of life, ECGs, OCT, and PFT.	
Scheduled Study Visit (Protocol Scheduled Day)	Analysis Visit Window (Study Day)
Baseline in Study APD334-302	≤ 1
Week 12 (Day 85 ± 3) ^b in Study APD334-302	66 to 113 (66 to 141 for assessments impacted by COVID-19 pandemic) ^c
Week 32 (Day 225 ± 7) [PFT only]	198 to 253 (198 to 281 for assessments impacted by COVID-19 pandemic) ^c
Week 52 (Day 365 ± 7) ^b	337 to 393 (337 to 421 for assessments impacted by COVID-19 pandemic) ^c

^a Applicable only for subjects who required extended monitoring on Day 2 for vital signs and ECGs.

^b Applicable to all Week 12 and Week 52 efficacy endpoints based on any component of Mayo clinic score, such as clinical remission and symptomatic remission. Protocol visit window for PFT and OCT at Week 12 is Day 85 ± 7 .

^c Assessments impacted by COVID-19 pandemic are reported in the Date of Visit eCRF.

ECG, electrocardiogram; eCRF, electronic case report form; MMS, modified Mayo score; OCT, optical coherence tomography; PFT, pulmonary function test; RB, rectal bleeding; SF, stool frequency

For cardiac remonitoring upon treatment reinitiation after Day 2, as manifested by more than 1 timed measurement in vital signs or electrocardiogram (ECG) parameters on the same collection date of an unscheduled visit, measurement will be mapped to analysis visit of Cardiac Remonitoring 1, Cardiac Remonitoring 2, etc. in the respective analysis dataset. For analysis, each timed measurement will be programmatically assigned to the nearest hourly timepoint (e.g., Predose, 1-hour Postdose) based on their relationship to the dosing time on the same day. If the dosing date/time on the same day is missing, the timepoint will remain missing. Once mapped, these timed measurements from cardiac remonitoring visits will not be considered for any other analysis visit.

Windowing will be applied prior to any missing data calculations. The last non-missing measurement taken prior to Day 1 (including unscheduled assessments) will be labeled as “Baseline”. Unless stated otherwise, data from all visits including scheduled, unscheduled, and ET visits will be eligible for allocation to an analysis visit. The 2-Week and 4-Week Follow-Up visits will not be included in the visit windows and will be summarized separately without any window applied.

If one or more results for a variable are assigned to the same analysis visit, the result with the date closest to the protocol scheduled day will be used in the analysis, except for component subscores of MMS or TMS, in which case, the composite score and component subscores from the same date will be used in the analysis. If 2 measurements in the same analysis visit window are equidistant from the protocol scheduled study day, the earliest measurement will be used in the analysis. If multiple assessments are available on the same day, then the average of the assessment will be used in the analysis, except for laboratory and ECG data where the

assessment at the earliest time of the same day will be used. If both central and local assessments of the same ECG or lab test are available on the same day, the central result will take precedence over the local result.

For the overlapping visit windows at Week 48 and Week 52, Week 52 will take priority.

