17. HEALTH-RELATED QUALITY OF LIFE AND HEALTHCARE RESOURCE UTILIZATION ANALYSIS

Subject reported HRQoL instruments will be electronically captured and used in support of the efficacy outcomes. All HRQoL are administered at Week 52/Early Termination Visit. The HRQoL analyses will be performed using the mFAS data as observed.

All HRQoL endpoints will be analyzed using descriptive statistics (n, mean, SD, median, minimum, and maximum)

Healthcare resource utilization endpoints, ie, the proportion of concomitant UC-related hospitalizations and the proportion of concomitant UC-related surgeries, including colectomy, will be analyzed using the analysis method described in Section 16.1.3.

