18.4. ECG EVALUATIONS

ECGs are recorded on a 12-lead ECG machine and read centrally. The following ECG parameters will be reported for this study:

- HR (bpm)
- RR Interval (msec)
- PR Interval (msec)

- QRS Interval (msec)
- QT Interval (msec)
- QTcF Interval (msec)
- Overall assessment of ECG (Investigator's judgment):
 - Normal
 - Abnormal, Not Clinically Significant (Abnormal NCS)
 - Abnormal, Clinically Significant (Abnormal CS)
- Overall interpretation of ECG (central reader):
 - Normal
 - Abnormal NCS
 - Abnormal CS
- AV conduction abnormalities
 - First-degree AV block
 - Second-degree AV block type 1
 - Second-degree AV block type 2
 - Third-degree AV block

The following summaries will be provided for ECG data:

- Value and change from Baseline by visit (for quantitative measurements)
- Incidence of markedly abnormal values (defined in [Section 18.4.1](#)) and AV blocks by visit
- Shift in normal/abnormal NCS/abnormal CS in the overall interpretation (by investigator) from Baseline to Week 52/Early Termination Visit and to the worst-case post-Baseline result
- Shift in markedly abnormal categories from Baseline to post-Baseline by visit

Listings of ECG results, including first dose cardiac monitoring, and discharge criteria for first dose cardiac monitoring will be provided.

A listing of all ECG assessments over time in subjects meeting markedly abnormal criteria will also be provided. For each subject, only ECG parameters ever meeting markedly abnormal criteria will be included.

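### HRQoL and quantitative ECG results from Early Termination visits on Days 114 to 336 have no analysis visit, so the Week 52 by-visit summaries leave those subjects out

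*SAP*

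**What the plan says.** For by-visit analyses, SAP 6.3 says of efficacy, safety, HRQoL and biomarker results: "data (including scheduled, retests, unscheduled, and early termination) will be assigned to visits after the application of the windowing conventions described in Section 6.4". SAP 6.4 repeats that Early Termination visits can be allocated to an analysis visit. The visit table in SAP Appendix 1 places Early Termination under whatever analysis visit it is assigned, so it has no separate row.

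Table 2 in SAP 6.4 has two blocks. The second covers endoscopy-based measures and also "physician's global assessment, health-related quality of life, ECGs, OCT, and PFT". Its Week 12 window is "66 to 113 (66 to 141 for assessments impacted by COVID-19 pandemic" and its Week 52 window is "337 to 393 (337 to 421 for assessments impacted by COVID-19 pandemic". HRQoL, ECG and OCT have no window between these two.

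On collection and summary:

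- **HRQoL.** SAP 17 states: "All HRQoL are administered at Week 52/Early Termination Visit". The analysis is descriptive, in the mFAS, using data as observed. SAP 17.2 rules out imputation.
- **ECG.** Protocol Table 7 schedules the 12-lead ECG in this study only at Week 52/Early Termination. SAP 18.4 plans "Value and change from Baseline by visit (for quantitative measurements"). It also plans markedly abnormal values and AV blocks by visit, and a shift in overall interpretation from Baseline to Week 52/Early Termination and to the worst post-Baseline result.
- **General rules.** SAP 6.3 lets all measurements count in abnormality and worst-case summaries, and requires listings to include Early Termination data.

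**The concern.** The Early Termination visit exists to capture a subject's status on leaving. Protocol 5.1 asks for it within 7 days of the last dose, whenever that falls. If the result lands between the two windows, the plan collects it and then gives it no place in the by-visit tables.

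Those who stop early are unlikely to be a random subset. Protocol 5.1 lists worsening disease, adverse events and lack of efficacy among the reasons for stopping, and Protocol 5.1.1 lets subjects with worsening disease move to the open-label study. A Week 52 HRQoL mean restricted to subjects assessed from Day 337 onward may look better than the experience of everyone treated, and the loss could differ between arms. For HRQoL no other summary brings these values back.

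There is also a gap in definitions. SAP 18.3.1 and 18.4 use Week 52/Early Termination as a shift-table endpoint, but Table 2 never defines it. A programmer could apply the windows strictly and drop the Early Termination result, or take the last on-treatment value. The SAP does not say which.

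**Working it through.** The plan gives no figure to reproduce. The check is to place each study day against the Table 2 windows quoted above.

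**1. HRQoL and ECG (and OCT).** The Week 12 window ends on Day 113 and the Week 52 window starts on Day 337.
- First uncovered day: 113 + 1 = 114. Last: 337 − 1 = 336. Length: 336 − 114 + 1 = 223 days, with no window inside.
- COVID-19-impacted: the Week 12 window extends to Day 141, so the gap is Days 142 to 336, or 336 − 142 + 1 = 195 days.

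**2. PFT.** Table 2 adds a row "Week 32 (Day 225 ± 7) [PFT only"] with window "198 to 253 (198 to 281 for assessments impacted by COVID-19 pandemic").
- Uncovered: Days 114–197 (84 days) and 254–336 (83 days), so 84 + 83 = 167 of the 223 days.
- COVID-19-impacted: Days 142–197 (56) and 282–336 (55), so 56 + 55 = 111.

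**3. Edges of the gap.** An Early Termination result on Days 337 to 364 (364 − 337 + 1 = 28 days) counts as Week 52. One before Day 114 falls in the Week 12 window, so it does not reach the Week 52 row either.

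**4. Comparison with the first block.** For laboratory tests and vital signs the windows run without a break from Day 72 (72–99, 100–127, 128–155, 156–197, 198–253, 254–309, 310–351, then above 351). The gap is specific to the second block.

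**5. One subject followed through.** Suppose the Early Termination visit is on Day 200 and is not COVID-19-impacted.

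| Step | HRQoL | ECG |
|---|---|---|
| In the analysis set | Yes: Baseline plus one post-enrollment value meets SAP 5.5 | Yes: Safety Set, SAP 5.6 |
| Analysis visit under Table 2 | None | None |
| Replacement value | None (SAP 17.2) | None (SAP 8.3) |
| Mean and change by visit | Absent | Absent |
| Abnormality or worst-case summary | None planned | Kept under SAP 6.3 |
| Shift table naming Early Termination | None planned | Interpretation shift, SAP 18.4 |
| Listing | Yes | Yes |

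**6. Scale.** From Day 85 to Day 365 there are 365 − 85 + 1 = 281 days, and 223/281 = 79% of them lie in the gap. That is a share of the calendar, not of the data.

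The weight of one subject can only be illustrated. Assume all of the approximately 35 planned subjects enroll:
- 2:1 split: 35 × 2/3 ≈ 23 and 35/3 ≈ 12. One such stop removes 1/23 ≈ 4% of the etrasimod arm or 1/12 ≈ 8% of the placebo arm from the Week 52 row.
- Near-even split (18 and 17): about 6% in either arm (1/18 and 1/17).

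The range matters because SAP 6.5 says central randomization was not designed to control the allocation ratio in Japan.

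**The case against.** The strongest defence is that this is a legitimate windowing choice. A value from, say, Day 150 does not belong in a Week 52 mean. HRQoL is supportive, descriptive and explicitly as observed. Treatment failure among early stoppers is already counted, because the responder endpoints use non-responder imputation (SAP 16.1.2 and 16.2.1). With about 35 subjects, listings can be read one subject at a time. SAP 2.5 also leaves the scope of outputs to the table, listing and figure shells, which are not among the documents and might already contain an end-of-treatment row.

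Most of this stands, and it is why the existing Week 52 row should stay as it is. It does not explain why the only HRQoL value that this study collects from an early stopper should enter no summary, nor what the combined Week 52/Early Termination endpoint means.

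Some stronger readings are not supported:

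- **A reader might infer that the Week 52 summaries hold only subjects who finish treatment.** Early Termination results on Days 337 to 364 count as Week 52.
- **A reader might extend the full gap to PFT.** Days 198 to 253 (to 281 if COVID-19-impacted) map to Week 32.
- **A reader might count PFT and OCT as losing data in practice.** SAP 18.7.2 presents only those PFT and OCT assessments completed by at least 50 subjects. About 35 are planned, so as written neither is summarised, whatever the windows.
- **A reader might infer that the ECG safety signal is lost.** SAP 6.3 keeps all measurements in abnormality and worst-case summaries. What drops out is the mean value and mean change. One loose end is that SAP 18.4 plans ECG abnormalities by visit and, unlike SAP 18.5 for vital signs, names no any-time row for a result without a window.
- **A reader might want a percentage lost per arm.** The documents give no discontinuation rates, so any such figure would only restate its own assumption.

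**Conclusion.** The gap is real for HRQoL and for quantitative ECG values. An Early Termination result on Days 114 to 336 (Days 142 to 336 if COVID-19-impacted) has no analysis visit and no row. The consequence is greatest for HRQoL, where the subject meets the mFAS rule but contributes to no summary. For ECG it is limited to by-visit means and changes.

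The number of subjects affected depends on how many Early Termination assessments fall in the gap, which is unknown before the data are seen. That the loss is informative, or differs by arm, is plausible from the listed reasons for stopping but is not shown by the documents.

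The primary, key secondary and other secondary responder endpoints are untouched. This is an inexpensive improvement to supportive and safety summaries, not a threat to the main result. It rests on reading SAP 6.3, SAP 6.4 and Appendix 1 as written. If the shells already define an end-of-treatment row, the change reduces to writing that definition into the SAP.

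**What to change.** Add to SAP Table 2, for HRQoL and ECG, an analysis visit labelled *End of treatment (Week 52 or Early Termination)*. Report it beside the existing Week 52 row, not in place of it. Use the same definition for the Week 52/Early Termination endpoint of the shift tables in SAP 18.3.1 and 18.4, so that the term has one meaning.

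Extend the row to PFT and OCT only if those measures are to be summarised, which first requires revisiting the 50-subject threshold in SAP 18.7.2. Leave the responder endpoints under non-responder imputation as they are.

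The cost is a short SAP edit and one extra row per affected table, with no new data collection. The drawback is that the row mixes assessment times, from shortly after Week 12 to Week 52. The table title or a footnote must say so, and the row should not be read as a Week 52 estimate.

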1.3. Benefit/Risk Assessment

Common adverse events that have been reported with S1P receptor modulators include bradycardia at the first dose or atrioventricular (AV) block, macular edema, hypertension, headache, cough, dyspnea, back pain, influenza, and diarrhea.

Safety and tolerability of etrasimod has been evaluated in Phase 1 studies with healthy adult subjects at single doses up to 5 mg and repeated doses up to 4 mg once daily. Repeated doses of 2 mg have been evaluated in Phase 2 studies of subjects with moderately to severely active UC (refer to the current edition of the IB). Etrasimod was found to be safe and well tolerated in these studies, with no clinically significant safety concerns with respect to vital signs, electrocardiograms (ECGs), pulmonary function tests (PFTs), ophthalmoscopy, or clinical laboratory tests. Etrasimod produced a dose-dependent sustained decrease in total lymphocyte count, which is expected given etrasimod's mechanism of action. Lymphocyte counts returned to approximately baseline levels within 7 days after the last dose.

Detailed information regarding the known and expected benefits and risks and reasonably expected adverse events of etrasimod can be found in the IB.

Based on the mechanism of action of etrasimod and prior experience with other agents acting via a similar mechanism, monitoring for specific safety parameters are planned for this study, which include: auscultation of the lungs as part of the physical exam; PFT; exclusion of subjects with macular edema or retinopathy, with assessment of optical coherence tomography (OCT) occurring throughout the study; and exclusion of subjects with certain cardiac risks, with assessment of vital signs in the period following dosing.

- Auscultation of lungs will be conducted as part of the physical examination.
- Prospective subjects with a history of macular edema or retinopathy will be excluded from the study. All randomized subjects will be assessed by OCT at study entry, periodically throughout the treatment period, and as clinically indicated any time during the study.
- Subjects with certain cardiac risks will also be excluded from the study. Randomized subjects will be monitored in a period following dosing, and vital signs will be assessed for determination of the subject's health before discharge. Subjects requiring follow-up monitoring will be evaluated in the clinic until cardiac variances return to acceptable levels.

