Because transient fluctuations of ALT or AST are common, and progression to severe drug-induced liver injury or acute liver failure is uncommon, automatic discontinuation of study treatment upon finding a greater than 3 × ULN elevation of ALT or AST may be unnecessary.

Subjects who discontinue treatment prematurely, regardless of the reason, should be instructed to return for an Early Termination visit within 7 days of the last study treatment administration (Table 7) and before initiation of any new treatments to complete all of the early termination assessments. If a subject discontinues due to pregnancy, they are not required to complete the endoscopy. If the Early Termination visit is within 4 weeks of the last sigmoidoscopy and biopsy, these procedures do not need to be repeated.

If the Early Termination visit is ≥ 2 weeks of the last dose of study treatment, the 2-Week Follow-Up visit is not required; however, the 4-Week Follow-Up visit should be scheduled and completed. If the Early Termination visit is ≥ 4 weeks of the last dose of study treatment, the 4-Week Follow-Up visit is not required unless the absolute lymphocyte count (ALC) is not within normal limits.

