The pharmacokineticist will determine the strategy for dealing with data affected by protocol deviations or events which may impact the quality of etrasimod concentration data on a case-by-case basis with input from the Arena study physician and Arena clinical pharmacologist, as needed. Examples for protocol deviations or events include, but may not be limited to, sample processing errors that lead to inaccurate bioanalytical results, and/or inaccurate dosing prior to PK sampling. In the case of an important protocol deviation or event, the affected PK data collected may be excluded from the summaries, calculation of the average steady-state trough plasma concentration ($C_{\text{trough,ss}}$) based on Week 16 to Week 52 trough concentrations ($C_{\text{trough,ss,W16-W52}}$), and population PK analysis, but will be reported in the study result listings.

Individual subject etrasimod plasma concentrations (and etrasimod metabolite concentrations, if applicable) will be presented in the data listings, including subject ID, treatment received, sex, age, weight, tobacco use, nominal timepoint, actual blood collection date/time, concentration, and time since last dose and also summarized using descriptive statistics (n, mean, SD, % CV, geometric mean, geometric % CV, median, minimum, and maximum) by nominal timepoint.

Individual subject steady-state trough (predose) plasma concentration will be averaged across Weeks 16 to 52 ($C_{\text{trough,ss,W16-W52}}$) and presented in a data listing and summarized using descriptive statistics.

Mean (\pm SD) etrasimod concentration versus nominal time (Weeks 16 to 52) will be plotted on linear scales. Plot will be repeated by sex (male and female).

Individual subject plasma etrasimod concentrations versus actual time (Weeks 16 to 52) will be plotted on linear scale.

Scatter plots of individual subject average steady-state $C_{\text{trough,ss,W16-W52}}$ versus Baseline body weight as a continuous variables will be generated for the Pharmacokinetic Set, which will also include the Spearman's rank correlation coefficient, p-value, and locally estimated scatterplot smoothing (LOESS) trend line.

Furthermore, the following overlay plots will be generated for the Pharmacokinetic Set within the etrasimod group only:

- Mean (SD) absolute lymphocyte counts and mean (SD) etrasimod concentration versus nominal timepoint (Weeks 16 through 52)

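### Early Termination lymphocyte counts are allocated to Week 16–52 windows regardless of time since last dose, so off-drug values can be summarized as on-treatment; how an Early Termination PK sample is treated is unspecified

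*SAP*

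**What the plan says.** **Allocation.** SAP 6.3 provides that "efficacy, safety, HRQoL, and biomarkers data (including scheduled, retests, unscheduled, and early termination) will be assigned to visits" by the conventions of Section 6.4. That section says the convention "will be applicable for all by-visit summaries and analyses for efficacy and safety data", and adds: "Unless stated otherwise, data from all visits including scheduled, unscheduled, and ET visits will be eligible for allocation to an analysis visit". The first block of Table 2 is headed "For all efficacy (except endoscopy/MMS/histology), efficacy-related biomarkers, safety labs and vital signs", so it covers lymphocyte counts. Where several results share a window, "the result with the date closest to the protocol scheduled day will be used in the analysis". Only the 2-Week and 4-Week Follow-Up visits are kept out of the windows. SAP Appendix 1 gives ET no study period of its own; it follows the assigned analysis visit.

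**Timing of ET.** Under Protocol 5.1, subjects who stop early should "return for an Early Termination visit within 7 days of the last study treatment administration". The same section provides for an ET visit 2 weeks or more after the last dose, in which case the 2-Week Follow-Up is not required. It makes a similar provision at 4 weeks.

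**Recovery.** Protocol 1.3: "Lymphocyte counts returned to approximately baseline levels within 7 days after the last dose".

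**PK.** SAP Section 20 lists predose samples at named weeks and summarizes them by nominal timepoint. It then says: "Individual subject steady-state trough (predose) plasma concentration will be averaged across Weeks 16 to 52". Protocol Table 7 puts Week 52 and ET in a single column that includes a PK sample.

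**The concern.** Section 19 uses the by-visit lymphocyte value, change and percent change to show the drug's pharmacodynamic effect during treatment. A count taken after the drug has stopped, and possibly after recovery, does not measure that effect. If it carries a Week 16–52 label, it pulls the etrasimod mean toward zero change. It also lowers the proportion below the lymphopenia cut-offs at Week 52 (SAP 18.3.1). A reader of the tables cannot see that this has happened.

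The rule is also inconsistent with itself. The SAP treats follow-up samples as off-treatment and reports them separately, but it windows a late ET visit that stands in for a follow-up visit.

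**Working it through.** **1. Reproduce Table 2 (biomarker and safety-laboratory block).** Scheduled days are 85, 113, 141, 169, 225, 281, 337 and 365. Midpoints of consecutive days:

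- (85+113)/2 = 99
- (113+141)/2 = 127
- (141+169)/2 = 155
- (169+225)/2 = 197
- (225+281)/2 = 253
- (281+337)/2 = 309
- (337+365)/2 = 351

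All seven match the stated upper bounds. The windows have no gaps from Day 72, and Week 52 is open-ended (> 351). No ET sample from Day 100 onward can fall outside a window.

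**2. How often an ET sample is allocated and used.** The Section 6.4 rule was applied to every last-dose day from 86 to 357 (272 days). Scheduled visits were assumed to fall exactly on their target day.

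| Days from last dose to ET | In a Week 16–52 window | Is the value analyzed |
|---|---|---|
| 1 | 95% | 49% |
| 3 | 96% | 54% |
| 5 | 97% | 59% |
| 7 | 97% | 64% |
| 14 | 100% | 82% |
| 28 | 100% | 99% |

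Pooled over gaps of 1 to 7 days, the ET sample is the analyzed value for 57% of combinations. These are shares of possible last-dose days, not predicted frequencies; the documents give no dropout pattern.

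**3. Displacement of an on-drug value.** Step 2 cannot show this, because it puts visits exactly on target. Suppose the Week 24 visit is on Day 165, within the permitted ±7 days of Day 169. The subject takes the last dose that day and attends ET on Day 172, 7 days later. Both days lie in the Week 24 window (156 to 197). The distances are |165 − 169| = 4 and |172 − 169| = 3, so the off-drug count replaces the on-drug one.

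**4. Same sample, two labels.** Last dose on Day 200, blood drawn on Day 200 + 14 = 214. Labelled 2-Week Follow-Up, it is reported separately. Labelled ET, it falls in the Week 32 window (198 to 253), and is analyzed there unless another result lies closer to Day 225.

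**5. Size.** About 35 subjects at 2:1 gives 35 × 2/3 ≈ 23 on etrasimod. The documents give no on-drug lymphocyte change, so a mean Δ of −40% to −60% is assumed. With m fully recovered values (0% change) among n, the mean is Δ × (n − m)/n.

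| Assumed Δ | m = 1 | m = 3 |
|---|---|---|
| −40% | −38.3% | −34.8% |
| −50% | −50 × 22/23 = −47.8% | −50 × 20/23 = −43.5% |
| −60% | −57.4% | −52.2% |

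**6. PK, by comparison of text.** SAP 6.3, 6.4 and Table 2 name efficacy, safety, HRQoL and biomarker data, not concentrations. Section 20 works by nominal timepoint. Table 7's combined column means an ET sample may carry the Week 52 label. Section 20 neither includes nor excludes it, and sets no maximum time since last dose. Its exclusion provision is case by case. No size can be calculated, because the documents give neither a half-life nor a number of ET samples.

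**The case against.** **ET does not always mean off-drug.** Protocol 3.1 pairs ET with the last on-treatment visit, the 7 days are a maximum, and Table 7 allows blinded drug to be dispensed to cover a gap before the open-label extension. ET visits at 2 or 4 weeks depart from the 7-day instruction. All of this stands. It argues for a rule based on time since last dose rather than a ban on ET values.

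**The closest-day rule already removes many ET values.** For gaps of 1 to 7 days, 36% to 51% are not the analyzed value in step 2. This stands too, but the rest are used, and step 3 shows the rule can work the wrong way.

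**The outputs are descriptive.** No primary or key secondary endpoint uses lymphocyte counts, and individual values are listed. This limits the importance of the point without removing it.

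**PK is protected elsewhere.** A reader might infer that washed-out concentrations will enter the steady-state trough average. The documents do not support that. The windowing text does not name PK. Table 7 defines predose as within 60 minutes before dosing, which a sample after permanent discontinuation cannot satisfy. SAP 5.7 and Section 20 both allow for events that affect concentration. What remains is that the ET case is unstated and exclusion is discretionary.

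**Conclusion.** The point holds for lymphocytes. As written, the SAP can report off-drug counts as Week 16–52 values, and it treats a late ET visit differently from the follow-up visit it replaces. With 23 etrasimod subjects and an assumed −50% change, one recovered value moves a window mean by about 2 percentage points and three by about 6.5. Full recovery is the extreme case for an ET visit only a day or two after the last dose. In the other direction, each value weighs more if fewer than 23 subjects remain in a window. The figure of 23 is itself approximate, because randomization was not controlled within Japan.

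For PK the finding is an unspecified rule, not demonstrated contamination. The concentration–lymphocyte overlay plots in Section 20 also use nominal timepoints, so contamination there is not shown either.

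Three further inferences are tempting but unsupported:

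- **Heart rate** shares the Table 2 block, but the documents give no recovery time for it.
- **Evening dosing** could make a predose sample fall mid-interval, but Protocol 6.3 prefers morning dosing and 9.1 prefers morning visits.
- **The end-of-treatment count** in the SAP 18.3.1 recovery shift could already be recovered, but the SAP does not define it as the ET value.

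**What to change.** **SAP 6.4 and 19.** Allocate a lymphocyte value to a Week 16–52 summary only if it was collected within a pre-specified short time of the last dose. Within a window, give on-treatment values precedence over later ones, ahead of the closest-day rule. Show later ET values separately, by days since last dose. ET values from subjects still dosing are kept. The sponsor should choose the limit and justify it from recovery data before unblinding.

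**SAP 20.** State that samples taken after treatment has stopped are not included in the Week 16–52 steady-state trough average, and whether an ET sample may be labelled Week 52. A narrow fixed trough interval such as 20 to 28 hours is not advised. Protocol 6.3.1 lets a forgotten dose be taken up to 8 hours late, so the next trough could properly fall at 24 − 8 = 16 hours.

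**Cost.** SAP wording and one programming flag. Last-dose dates are collected on the eCRF (SAP 14.1), and the time of the last dose is documented for every PK draw (Protocol Table 7). The downside is a few fewer values per visit.
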